xxxxxxx	xx	ddmmmyyyy (Day x)	1/2/3	xx, Gx	Yes; Mild / Moderate/ Severe	Yes; Mild / Moderate / Severe	Yes; Mild/ Moderate/ Severe	Yes; Mild/ Moderate / Severe No	Yes	Yes; Yes	Xx; Xxxx Xxxxx

Abbreviations: HPV = Human Papillomavirus.

Programming Notes

Output ID: LS0014

[Source: \quintiles.net\Enterprise\Apps\sasdata\SASb\SAS\GlaxoSmithKline\HPV\213749

(HPV9) \Biostatistics\Filename.sas] IQVIA DDMMMYYYY HH:MM

\\quintiles.net\Enterprise\Apps\sasdata\SASb\SAS\GlaxoSmithKline\HPV\213749 (HPV9)\Biostatistics\Documentation\SAP\Shells\ Document: GSK 213749(HPV9-AS04-001)_WZA97329_TFL Shells_V3.0_05FEB2024.docx

Version Number: 3.0 Author:

Listing 16.2.7.3: Unsolicited Adverse Events (Enrolled Set)

GSK Vaccines Page X of Y

Study 213749 - DELIVERY DESIGNATION

Listing 16.2.7.3
Unsolicited Adverse Events
Enrolled Set

Vaccine Group: HPV9 High / HPV9 Medium / HPV9 Low / Gardasil 9

Participant Identifier	Site ID	System Organ Class; Preferred Term; AE term (Vaccine Dose)	Start Date (Onset Day); End Date (Study Day)	Duration (Days)	Severity; Relationship to Study Treatment	Action Taken to Study Drug; Outcome	Potential Immune- Mediated Disease (pIMD) event?	Serious; If yes, Criteria	Medical Attention	COVID19?	Treatment Given? If Yes, Treatment
xxxxxxx	xx	xxxxxxxxx; xxxxxxxxx; xxxxxx (x)	ddmmmyyyy (x); ddmmmyyyy (x)	xx	Mild / Moderate/ Severe; Related / Not Related	xxxxx; xxxxxxx	Yes	Yes; xxxx	Yes	Yes	No Yes; xxxx

Abbreviations: HPV = Human Papillomavirus. COVID19 = Coronavirus disease 2019. MedDRA = Medical dictionary for regulatory activities.

MedDRA version xx.x.

Unsolicited AEs include serious AEs.

Programming Notes

Output ID: LS0015

[Source: \quintiles.net\Enterprise\Apps\sasdata\SASb\SAS\GlaxoSmithKline\HPV\213749

(HPV9) \Biostatistics\Filename.sas] IQVIA DDMMMYYYY HH:MM

Document: \\quintiles.net\Enterprise\Apps\sasdata\SAS\SAS\GlaxoSmithKline\HPV\213749 (HPV9)\Biostatistics\Documentation\SAP\Shells\

GSK 213749(HPV9-AS04-001)_WZA97329_TFL Shells_V3.0_05FEB2024.docx

Author: Version Number: 3.0

GlaxoSmithKline Biologicals SA PROTOCOL 213749 (HPV9)

Document:

Version Number: 3.0 Author:

05FEB2024 Version Date:

Listing 16.2.7.4: Unsolicited Adverse Events Leading to Withdrawal or Discontinuation from Study (Enrolled Set)

GSK Vaccines Page X of Y

Study 213749 - DELIVERY DESIGNATION

Vaccine Group: HPV9 High / HPV9 Medium / HPV9 Low / Gardasil 9 Potential Start Date System Organ (Onset Action Immune-Mediated Class; Day); End Taken to Severity; Treatment Preferred Term; Date Relationship Study Disease Serious; Given? If Participant Site (Study Duration to Study Drug; (DMIq) If yes, Medical AE term Yes, Identifier ID (Vaccine Dose) Day) (Days) Treatment Outcome event? Criteria Attention COVID19? Treatment Mild / ddmmmyyyy Yes No xxxxxx; Moderate/ (x); XXXXXXXX XXXXXXXXXX; Severe; XXXXXXX XX xxxxxxxxx; ddmmmyyyy XX Yes Yes; xxxx Yes Related / xxxxxx (x) (x) Not Related No No No Yes; xxxx

Abbreviations: HPV = Human Papillomavirus. COVID19 = Coronavirus disease 2019. MedDRA = Medical dictionary for regulatory activities.

MedDRA version xx.x.

Unsolicited AEs include serious AEs.

Programming Notes

Output ID: LS0016

[Source: \quintiles.net\Enterprise\Apps\sasdata\SASb\SAS\GlaxoSmithKline\HPV\213749

(HPV9)\Biostatistics\Filename.sas| IOVIA DDMMMYYYY HH:MM

Document: \\quintiles.net\Enterprise\Apps\sasdata\SASb\SAS\GlaxoSmithKline\HPV\213749 (HPV9)\Biostatistics\Documentation\SAP\Shells\

GSK 213749(HPV9-AS04-001) WZA97329 TFL Shells V3.0 05FEB2024.docx

Author: Version Number: 3.0

Listing 16.2.7.5: Serious Adverse Events (Enrolled Set)

GSK Vaccines Page X of Y

Study 213749 - DELIVERY DESIGNATION

Listing 16.2.7.5 Serious Adverse Events Enrolled Set

Vaccine Group: HPV9 High / HPV9 Medium / HPV9 Low / Gardasil 9

		System Organ Class;		
Participant		Preferred Term;		
Identifier	Site ID	AE Term (Vaccine Dose)	Country	
				•
		xxxxxxxxxxxxxxx;		
		xxxxxxxxxxxxxx;		
XXXXXXX	XX	xxxxxxxxxxxxx (x)	XXXXXXXXX	

Abbreviations: HPV = Human Papillomavirus. Serious AEs are expedited adverse events.

Programming Notes

Output ID: LS0017

[Source: \quintiles.net\Enterprise\Apps\sasdata\SASb\SAS\GlaxoSmithKline\HPV\213749

(HPV9) \Biostatistics\Filename.sas] IQVIA DDMMMYYYY HH:MM

\\quintiles.net\Enterprise\Apps\sasdata\SASb\SAS\GlaxoSmithKline\HPV\213749 (HPV9)\Biostatistics\Documentation\SAP\Shells\ Document: GSK 213749(HPV9-AS04-001)_WZA97329_TFL Shells_V3.0_05FEB2024.docx

Version Number: 3.0 Author: Version Date: 05FFB2024

Listing 16.2.7.6: All Serious Adverse Events Leading to Withdrawal or Discontinuation from Study (Enrolled Set)

GSK Vaccines Page X of Y

Study 213749 - DELIVERY DESIGNATION

Vaccine Group: HPV9 High / HPV9 Medium / HPV9 Low / Gardasil 9

Participant		System Organ Class; Preferred Term;		
Identifier	Site ID	AE Term (Vaccine Dose)	Country	
		xxxxxxxxxxxxxxxx;		
		xxxxxxxxxxxxxx;		
XXXXXXX	XX	xxxxxxxxxxxxx (x)	XXXXXXXX	

Abbreviations: HPV = Human Papillomavirus. Serious AEs are expedited adverse events.

Programming Notes

Output ID: LS0018

[Source: \\quintiles.net\Enterprise\Apps\sasdata\SASb\SAS\GlaxoSmithKline\HPV\213749

(HPV9) \Biostatistics\Filename.sas] IQVIA DDMMMYYYY HH:MM

Document: \\quintiles.net\Enterprise\Apps\sasdata\SAS\SAS\GlaxoSmithKline\HPV\213749 (HPV9)\Biostatistics\Documentation\SAP\Shells\

GSK 213749(HPV9-AS04-001)_WZA97329_TFL Shells_V3.0_05FEB2024.docx

Author: Version Number: 3.0

Listing 16.2.7.7: Potential Immune-Mediated Disease Events (Enrolled Set)

GSK Vaccines Page X of Y

Study 213749 - DELIVERY DESIGNATION

Vaccine Group: HPV9 High / HPV9 Medium / HPV9 Low / Gardasil 9

		System Organ Class;		
Participant		Preferred Term;		
Identifier	Site ID	AE Term (Vaccine Dose)	Country	
		xxxxxxxxxxxxxxxxxxxxxxxxxxxxxxxxxxxxxx		
		xxxxxxxxxxxxxxx;		
XXXXXXX	XX	xxxxxxxxxxxxx (x)	XXXXXXXXX	

Abbreviations: HPV = Human Papillomavirus.

Programming Notes

Output ID: LS0019

Author:

[Source: \quintiles.net\Enterprise\Apps\sasdata\SASb\SAS\GlaxoSmithKline\HPV\213749

(HPV9)\Biostatistics\Filename.sas] IQVIA DDMMMYYYY HH:MM

Document: \(\quintiles.net\Enterprise\Apps\sasdata\SASb\SAS\GlaxoSmithKline\HPV\213749\) (HPV9)\Biostatistics\Documentation\SAP\Shells\\
GSK\\\ 213749\(\text{HPV9-AS04-001}\) \(\text{WZA97329}\) \(\text{TFL Shells}\\\ \text{V3.0}\) \(\text{05FEB2024.docx}\)

PPD Version Number: 3.0

Listing 16.2.8.1: Laboratory Results (Enrolled Set)

GSK Vaccines Page X of Y

Study 213749 - DELIVERY DESIGNATION

Listing 16.2.8.1 Laboratory Results Enrolled Set

Vaccine Group: HPV9 High / HPV9 Medium / HPV9 Low / Gardasil 9

Participant Identifier	Site ID	Visit	Collection date	Lab test	Result	Unit	Reference Range	Investigator assessment	Grade
xxxxxxx	xx	Visit 1 Visit 2	ddmmmyyyy	Leukocytes Erythrocyte Hemoglobin Platelets Neutrophils Lymphocytes Monocytes Eosinophils Basophils BUN AST ALT	xx	xx	Xx - xx No	Normal Abnormal, not clinically significant Abnormal, clinically significant	Grade 1 Grade 2 Grade 3 Grade 4

Abbreviations: HPV = Human Papillomavirus.

Programming Notes

Output ID: LS0020

[Source: \\quintiles.net\Enterprise\Apps\sasdata\SASb\SAS\GlaxoSmithKline\HPV\213749

(HPV9) \Biostatistics\Filename.sas | IOVIA DDMMMYYYY HH:MM

\\quintiles.net\Enterprise\Apps\sasdata\SASb\SAS\GlaxoSmithKline\HPV\213749 (HPV9)\Biostatistics\Documentation\SAP\Shells\ Document: GSK 213749(HPV9-AS04-001)_WZA97329_TFL Shells_V3.0_05FEB2024.docx

Version Number: 3.0 Author:

Listing 16.2.8.2: Pregnancies - Follow up Report (Enrolled Set)

GSK Vaccines Page X of Y

Study 213749 - DELIVERY DESIGNATION

Listing 16.2.8.2

Pregnancies - Follow up Report
Enrolled Set

Vaccine Group: HPV9 High / HPV9 Medium / HPV9 Low / Gardasil 9

Participant Identifier	Site ID	Pregnancy outcome	Date of outcome	Method used for delivery	Number of neonates	Gestational weeks at birth / miscarriage / termination
xxxxxxx	xx	Live infant, no apparent congenital anomaly Live infant congenital anomaly Elective termination, no apparent congenital anomaly Elective termination congenital anomaly Spontaneous abortion, no apparent congenital anomaly Spontaneous abortion congenital anomaly Spontaneous abortion congenital anomaly Stillbirth, no apparent congenital anomaly Stillbirth congenital anomaly Ectopic pregnancy Molar pregnancy Lost to follow-up Pregnancy ongoing	ddmmmyyyy	Normal vaginal Caesarean section Forceps delivery Vacuum delivery	xx	xx

Abbreviations: HPV = Human Papillomavirus.

Programming Notes

Document: \\quintiles.net\Enterprise\Apps\sasdata\SAS\SAS\GlaxoSmithKline\HPV\213749 (HPV9)\Biostatistics\Documentation\SAP\Shells\

GSK 213749(HPV9-AS04-001)_WZA97329_TFL Shells_V3.0_05FEB2024.docx

Author: Version Number: 3.0

GlaxoSmithKline Biologicals SA PROTOCOL 213749 (HPV9)

Output ID: LS0021

[Source: \\quintiles.net\Enterprise\Apps\sasdata\SASb\SAS\GlaxoSmithKline\HPV\213749

(HPV9) \Biostatistics\Filename.sas] IQVIA DDMMMYYYY HH:MM

Document: \\quintiles.net\Enterprise\Apps\sasdata\SAS\SAS\GlaxoSmithKline\HPV\213749 (HPV9)\Biostatistics\Documentation\SAP\Shells\

GSK 213749(HPV9-AS04-001)_WZA97329_TFL Shells_V3.0_05FEB2024.docx

Author: Version Number: 3.0

Listing 16.2.8.3: Vital Signs (Enrolled Set)

GSK Vaccines Page X of Y

Study 213749 - DELIVERY DESIGNATION

Listing 16.2.8.3 Vital Signs Enrolled Set

Vaccine Group: HPV9 High / HPV9 Medium / HPV9 Low / Gardasil 9

Participant Identifier	Site ID	Visit	Assessment date	Parameter (unit)	Result
Identifier	DICE ID	VISIC	date	rarameter (unit)	Nesure
xxxxxxx	xx	Day 1 Month 1 Month 2	ddmmmyyyy	Systolic Blood Pressure (mmHg) Diastolic Blood Pressure (mmHg) Heart rate (bpm)	xx
		Month 3 Month 6		Respiratory rate (breathes/min)	
		Month 7			
		Month 12			

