Blood sample collection:

- A 5 mL blood sample will be drawn from Step 1 (Sentinel) participants at Visit 1 (Day 1) and Visit 2 (Day 7) to assess biochemical and hematological parameters.
- For assessment of immune response, blood samples (~50 mL) will be drawn at Day 1, Month 2, Month 3, Month 6, Month 7 and Month 12 in all participants. Immunoglobulin G (IgG) antibody determination will be performed for these timepoints in all participants. Pseudovirion-based neutralization assays will be performed. Blood samples drawn at Day 1 (all participants), Month 2 (at least 96 participants in each group), Month 3 (all participants) and Month 7 (at least 150 participants in each group) will be tested.

Study	Number of	Number of Age	Study	Blinding*	
groups	participants	(Min-Max)	vaccinations	Visit 1 to Visit 7 (Observer- Blind)	
HPV9High	270	16-26 years of age	HPV9-High	X	
HPV9Med	270	16-26 years of age	HPV9-Medium	X	
HPV9Low	270	16-26 years of age	HPV9-Low	X	
Gar9	270	16-26 years of age	Gardasil 9	X	

Table 5 Study Groups, Vaccines, and Blinding

Note: In Germany, only adult participants between and including 18 to 26 years of age will be included in this clinical study.

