APPENDIX 3 CLINICAL LABORATORY TESTS

For assessment of immune response, blood sample will be drawn at Day 1, Month 2, Month 3, Month 6, Month 7 and Month 12 in all participants. IgG antibody determination by ECL multiplex methodology will be performed for all timepoints in all participants.

Pseudovirion-Based Neutralization Assays (PBNA) will be performed on the following subsets: Day 1 (all participants), Month 2 (in a subset of 384 participants from Step 2 [96 participants in each group]), Month 3 (all participants) and Month 7 (at least 150 participants in each group from Step 2).

For these participants collection of an additional blood sample is foreseen at Day 1 and one month after the third dose (Month 7).

Humoral Immunity

Humoral Immunity: HPV IgG concentration by multiplex immunoassay (ECL)

The anti-HPV-6/11/16/18/31/33/45/52/58 IgG response will be measured using the ECL multiplex technology from [CC]

The HPV9-AS04 ECL assay will be qualified prior the clinical testing of this study, meaning that the assay performance characteristics will be assessed, including limit of detection, precision, linearity, accuracy, specificity, robustness and stability.

The assay qualification report and assay Standard Operation Procedure will be submitted to the Investigational New Drug application when available.

The assay will be performed at GSK, Clinical Laboratory Sciences (Rixensart/Wavre, Belgium).

Humoral Immunity: HPV neutralizing assay (PBNA)

The neutralizing antibodies will be determined by the PBNA for HPV-6/11/16/18/31/33/45/52/58 performed at the with some adaptations (secondary endpoint). The PBNAs for the 9 HPV types will be qualified at prior the clinical testing of the phase 1/2 study, meaning that assay performance characteristics including limit of

The assay qualification report and assay Standard Operation Procedure will be submitted to the IND when available.

detection, precision, linearity, specificity, robustness and stability will be assessed.

The assay will be performed by Germany.

APPENDIX 4 ADVERSE EVENTS: DEFINITIONS AND PROCEDURES FOR RECORDING, EVALUATING, FOLLOW-UP, AND REPORTING

Definition of an AE

An AE is any untoward medical occurrence (an unfavorable/unintended sign - including an abnormal laboratory finding), symptom, or disease (new or exacerbated) in a clinical study participant that is temporally associated with the study intervention. The AE may or may not be considered related to the study intervention.

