6.4. Per Protocol Set [PPS]

A per-protocol set (PPS) will be defined for all participants in the ES at each visit that meet the following criteria:

- Meeting all eligibility criteria
- For whom the administration route of the vaccine was as according to protocol
- For whom the study vaccine was administered per protocol
- Who did not receive a concomitant medication/product/vaccine leading to exclusion from a PP analysis, as
 described in the protocol
- Who did not present with an intercurrent medical condition leading to exclusion from a PP analysis, as described in the protocol
- Who complied with the vaccination schedule
- Who complied with the timings of the post-vaccination blood sampling for immune response evaluation
- For whom post-vaccination immunogenicity results are available for at least one antigen at the corresponding time points

The eliminations for the PPS will be adapted as per the timepoint analysis, e.g., for month 3 analysis only violations up to month 3 will be excluded.

Document: \\quintiles.net\Enterprise\Apps\sasdata\SAS\\SAS\GlaxoSmithKline\HPV\213749

(HPV9)\Biostatistics\Documentation\SAP\GSK_213749(HPV9-AS04-

001)_WZA97329_SAP_Final_v3.0_02FEB2024.docx

Author: PPD Version Number: 3.0

Version Date: 02FEB2024

Template No.: CS_TP_BS016 Revision 7 Reference: CS_WI_BS005

Page 26 of 48

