16.2.1.4. ANTI-HPV NEUTRALIZING ANTIBODY SEROCONVERSION AND SEROPOSITIVITY RATE

Anti-HPV neutralizing antibody seroconversion and seropositivity rates at Day 1 (seropositivity only), Month 3 and Month 7 (at least 150 participants in each group) and Month 2 in a subset of 384 participants (at least 96 in each group) for each antigen.

Seroconversion is defined as the appearance of antibodies (i.e, titer greater than or equal to the cut-off value) in the serum of participants seronegative before vaccination.

Seropositivity is defined as the appearance of antibodies (i.e, titer greater than or equal to the cut-off value) in the serum of participants.

16.2.1.5. CORRELATION BETWEEN ANTI-HPV IGG ANTIBODY CONCENTRATION AND ANTI-HPV NEUTRALIZING ANTIBODY TITERS

Correlation between anti-HPV IgG antibody concentrations and anti-HPV neutralizing antibody titers at Day 1, Month 2, Month 3, Month 7 and overall for each antigen.

Document: \\quintiles.net\Enterprise\Apps\sasdata\SASb\SAS\GlaxoSmithKline\HPV\213749

(HPV9)\Biostatistics\Documentation\SAP\GSK_213749(HPV9-AS04-

001)_WZA97329_SAP_Final_v3.0_02FEB2024.docx

Author: PPD Version Number: 3.0

Version Date: 02FEB2024

Template No.: CS_TP_BS016 Revision 7 Reference: CS_WI_BS005

Page 36 of 48

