Month 2	Seronegative	N	Х	Х	x	Х
		n (%)	xx (xx.x)	xx (xx.x)	xx (xx.x)	xx (xx.x)
		95% CI seropositivity	x.x - x.x	x.x - x.x	x.x - x.x	x.x - x.x
		GMT (GSD)	x.x (x.xx)	x.x (x.xx)	x.x (x.xx)	x.x (x.xx)
		Median	X . X	X • X	X.X	X.X
		Min - Max	x - x	x - x	x - x	x - x
		95% CI GMT	x.x - x.x	x.x - x.x	x.x - x.x	x.x - x.x
		n > ULOQ	xx (xx.x)	xx (xx.x)	xx (xx.x)	xx (xx.x)
Etc.		- · · · · ·	, ,	,	,	, ,

Source: Listing xx.x.x.x

Abbreviations: HPV = Human Papillomavirus. GMT = Geometric Mean Titer. GSD = Geometric Standard

Deviation. LLOQ = Lower Limit of Quantification. ULOQ = Upper Limit of Quantification.

 ${\tt N}$ = number of participants in the Per Protocol Set at each visit and pre-vaccination status.

n (%) = number/percentage of participants with titer equal or above LLOQ.

95% CI GMT = 95% confidence interval derived using the log10-transformed antibody titers.

Seronegative is defined as the situation where antibodies are not elevated (i.e, titers less than the LLOQ) in the serum of participants.

Seropositive is defined as the appearance of antibodies (i.e, titers greater than or equal to the LLOQ) in the serum of participants.

The titer below the LLOQ will be replaced by half the LLOQ (LLOQ/2). Titer above the ULOQ will be replaced by the ULOQ.

Programming Notes

Programming Notes

Output ID: IM0005

[Source: \quintiles.net\Enterprise\Apps\sasdata\SASb\SAS\GlaxoSmithKline\HPV\213749

(HPV9)\Biostatistics\Filename.sas] IQVIA DDMMMYYYY HH:MM

Document: \\quintiles.net\Enterprise\Apps\sasdata\SASb\SAS\GlaxoSmithKline\HPV\213749 (HPV9)\Biostatistics\Documentation\SAP\Shells\

GSK 213749(HPV9-AS04-001)_WZA97329_TFL Shells_V3.0_05FEB2024.docx

Author: Version Number: 3.0

Table 14.2.2.4.1: Ratio of anti-HPV Neutralizing Antibody GMTs for each antigen at Month 3 and Month 7 between Groups (HPV group [different potencies - Low, Med, High] divided by Gardasil 9 group) (Per Protocol Set)

GSK Vaccines Page X of Y

Study 213749 - DELIVERY DESIGNATION

Table 14.2.2.4.1

Ratio of anti-HPV Neutralizing Antibody GMTs for each antigen at Month 3 and Month 7 between Groups (HPV group [different potencies - Low, Med, High] divided by Gardasil 9 group)

Per Protocol Set

Antigen: xxx Pre-	(LLOQ = xx; ULOQ = xx; Unit = xx)						
vaccination		Н	PV9 Group	Gard	lasil 9 Group	Group	GMT Ratio
status		N	Adjusted GMT	N	Adjusted GMT	Value	95% CI
Seronegative	anti-HPV Neutralizing titer at Month 3						
beronegaerve	HPV9 High / Gardasil 9	XX	XX.X	XX	XX.X	XX.X	xx.x; xx.x

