The titer below the LLOQ will be replaced by half the LLOQ (LLOQ/2). Titer above the ULOQ will be replaced by the ULOO.

Programming Notes

Programming Notes

[Source: \\quintiles.net\Enterprise\Apps\sasdata\SASb\SAS\GlaxoSmithKline\HPV\213749

(HPV9)\Biostatistics\Filename.sas] IQVIA DDMMMYYYY HH:MM

Output ID: IM0013

Author: Version Number: 3.0

Table 14.2.2.5: Differences of anti-HPV Neutralizing Antibody Seroconversion Rate for each antigen at Month 3 and Month 7 between Groups (HPV group [different potencies - Low, Med, High] and Gardasil9 group) (Per Protocol Set)

GSK Vaccines Page X of Y

Study 213749 - DELIVERY DESIGNATION

Table 14.2.2.5

Differences of anti-HPV Neutralizing Antibody Seroconversion Rate for each antigen at Month 3 and Month 7 between Groups (HPV group [different potencies - Low, Med, High] and Gardasil9 group) Per Protocol Set

Antigen: xxx (LLOQ = xx; ULOQ = xx; Unit = xx)

	First	t Study Group	Secor	nd Study Group	Di	fference
	N	n (%)	N	n (%)	%	95% CI
Seroconversion Rate at Month 3						
HPV9 High - Gardasil 9	XX	xx (xx.x)	XX	xx (xx.x)	XX.X	xx.x; xx
HPV9 Medium - Gardasil 9	XX	xx (xx.x)	XX	xx (xx.x)	XX.X	xx.x; xx
HPV9 Low - Gardasil 9	XX	xx (xx.x)	XX	xx (xx.x)	XX.X	xx.x; xx
HPV9 High - HPV9 Low	XX	xx (xx.x)	XX	xx (xx.x)	XX.X	xx.x; xx
HPV9 Medium - HPV9 Low	XX	xx (xx.x)	XX	xx (xx.x)	XX.X	xx.x; xx
HPV9 High - HPV9 Medium	XX	xx (xx.x)	XX	xx (xx.x)	XX.X	xx.x; xx
Seroconversion Rate at Month 7						
HPV9 High - Gardasil 9	XX	xx (xx.x)	XX	xx (xx.x)	XX.X	xx.x; xx
HPV9 Medium - Gardasil 9	XX	xx (xx.x)	XX	xx (xx.x)	XX.X	xx.x; xx
HPV9 Low - Gardasil 9	XX	xx (xx.x)	XX	xx (xx.x)	XX.X	xx.x; xx
HPV9 High - HPV9 Low	XX	xx (xx.x)	XX	xx (xx.x)	XX.X	xx.x; xx
HPV9 Medium - HPV9 Low	XX	xx (xx.x)	XX	xx (xx.x)	XX.X	xx.x; xx
HPV9 High - HPV9 Medium	XX	xx (xx.x)	XX	xx (xx.x)	XX.X	xx.x; xx

Source: Listing xx.x.x.x

Abbreviations: HPV = Human Papillomavirus.

Document:

\\quintiles.net\Enterprise\Apps\sasdata\SAS\SAS\GlaxoSmithKline\HPV\213749 (HPV9)\Biostatistics\Documentation\SAP\Shells\ GSK 213749(HPV9-AS04-001)_WZA97329_TFL Shells_V3.0_05FEB2024.docx

Version Number: 3.0 Author:

N = Number of participants with available results who were seronegative (i.e, concentrations less than the LLOQ) at

n (%) = number/percentage of participants with concentration equal or above specified value.

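### Table 14.2.2.3 counts the whole Per Protocol Set as its denominator, so Month 2 neutralizing positivity would read about 36-44% even if every woman tested is positive; Month 7 is affected only while testing is incomplete

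*SAP*

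**What the plan says.** **The shell.** The footnotes to Table 14.2.2.3 define N as the "number of participants in the Per Protocol Set at each visit and pre-vaccination status" and then give "n (%) = number/percentage of participants with titer equal or above LLOQ". The table prints these, with a confidence interval for seropositivity and a count above the ULOQ, by visit and baseline serostatus. The baseline-seronegative rows after vaccination are in effect seroconversion rates.

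**Who is in the PPS.** Under SAP 6.4 the result criterion is: "For whom post-vaccination immunogenicity results are available for at least one antigen at the corresponding" time points. No assay is named. Protocol 4.1 has IgG measured in all participants at every immunogenicity visit, so an IgG result alone satisfies it.

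**Who is tested by PBNA.** Protocol 4.1 has all participants tested at Day 1, then "Month 2 (at least 96 participants in each group), Month 3 (all participants) and Month 7 (at least 150 participants in each group"). Protocol Appendix 3 describes the first of these as "Month 2 (in a subset of 384 participants from Step 2 [96 participants in each group"]. For Month 7, the endpoint lists in the Synopsis and Protocol Section 3 refer to all participants, with a footnote that sets 150 per group as a minimum and defers remaining samples to the next analysis.

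**What the rest of the SAP does.** SAP 16.2.1.4 specifies the neutralizing rates for "Month 2 in a subset of 384 participants (at least 96 in each" group), and 16.2.3.4 repeats this for the analysis. The GMT-ratio shells (Tables 14.2.2.4.1 and 14.2.2.4.2) count only participants with available results. The seroconversion-difference shell (Table 14.2.2.5) has "N = Number of participants with available results who were seronegative (i.e, concentrations less than the LLOQ") at baseline.

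**The concern.** A percentage needs numerator and denominator drawn from the same people. Here the numerator can come only from women with a PBNA titer, while the denominator takes in women whose sample was never assayed. At Month 2 that is more than half of each group. The printed percentage would then largely measure testing coverage, and the exact interval would be tight around the wrong value.

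In the shells shown, Table 14.2.2.3 is the only place where Month 2 neutralizing seroconversion appears, and the only one giving within-group neutralizing seropositivity with its interval. Protocol Amendment 3 enlarged the Month 2 subset to learn more about the response after the first dose. A reader who compared a diluted figure with the IgG rates in Table 14.2.1.1 could conclude that one dose neutralizes poorly when the data show no such thing.

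**Working it through.** **Inputs**
- Randomized per group: 270 (Protocol 9.2). Non-evaluable: 20%. Evaluable: 216 per group for the primary immunogenicity objective, which is at Month 7 (Protocol 9.2.2).
- Month 2 PBNA: 384 in total. Since 4 × 96 = 384, the minimum of 96 per group is also the number per group.
- Month 7 PBNA: at least 150 tested, to give 120 evaluable (Protocol 9.2.2.1).

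**Reproducing the plan's figures.** 270 × 0.8 = 216 and 150 × 0.8 = 120, both as stated. The protocol attaches at least 74% power to the 120. With log10 SD 0.6, margin 0.5 and two-sided 95% intervals:
- standardized difference: log10(2) / (0.6 × √(2/120)) = 0.301 / 0.0775 = 3.89
- power per HPV type: 97.3% (normal) or 97.2% (noncentral t)
- summing type II error over nine types: 1 − 9 × 0.0270 = 75.7%, or 1 − 9 × 0.0280 = 74.8%

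This agrees with the stated figure, so 120 and 216 are the protocol's own planning counts.

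**Literal footnote.** Suppose every tested woman is positive. The printed rate is (tested women in the PPS) / (PPS size), with PPS size taken as 216. The upper tested count assumes that all tested women are in the PPS; the lower one applies the 20% loss to them as well (96 × 0.8 = 76.8, about 77; 150 × 0.8 = 120). Intervals are Clopper-Pearson. When all n are positive the lower limit is 0.025^(1/n).

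| Visit | Literal shell | Available-result denominator |
|---|---|---|
| Month 2, 77 results | 77/216 = 35.6% (29.3-42.4) | 77/77 = 100% (lower limit 95.3) |
| Month 2, 96 results | 96/216 = 44.4% (37.7-51.3) | 96/96 = 100% (lower limit 96.2) |
| Month 7 minimum, 120 results | 120/216 = 55.6% (48.7-62.3) | 120/120 = 100% (lower limit 97.0) |
| Month 7 minimum, 150 results | 150/216 = 69.4% (62.8-75.5) | 150/150 = 100% (lower limit 97.6) |
| Month 7, all tested | 216/216 = 100% (lower limit 98.3) | the same |

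**Month 3.** PBNA is planned for all participants, so the final table has no subset dilution. However, Protocol 9.5.1 and SAP 5.2 allow the first interim analysis to proceed with at least 150 PBNA results per group at this visit. Until testing is complete, Month 3 has the same problem.

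**What is not touched.** SAP 7.6 computes GMTs from observed values and SAP 8.3 does not impute missing results, so GMTs are unaffected. The GMT ratios and seroconversion differences already use available results.

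**The case against.** The best defence is that the SAP text already settles the matter. Section 16.2.3.4 confines the Month 2 rates to the 384-woman subset, and 8.3 rules out imputing missing immunogenicity data, which treating untested women as negative would in effect do. Table 14.2.2.3 also lacks the explicit line, found in many other shells, that percentages are 100 × n/N; the denominator has to be inferred from its N and n (%) legends. A careful programmer might therefore do the right thing, and a mismatch might be caught on output review, because Table 14.2.2.8 prints the PBNA positive percentage at Month 2 among samples with both results. All of that is fair as evidence of intent. It does not remove the conflict: the footnote and 16.2.3.4 cannot both be followed, and the footnote is the more specific programming instruction.

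Three stronger readings are tempting, and the documents do not support them:
- **That Month 7 is certainly diluted.** Protocol 4.1 and Appendix 3 give only a minimum for Month 7, and Appendix 3 lists it among the PBNA subsets. But the endpoint lists say all participants, and 150 per group is a minimum throughout. Protocol 9.2.2.1 also gives power for 216 evaluable. The 56-69% is the figure at that minimum.
- **That the secondary neutralizing seroconversion endpoint is lost.** The protocol defines it at Months 3 and 7 only; the Month 2 rate is a SAP addition. The between-group comparison at Months 3 and 7 (Table 14.2.2.5) has the right denominator.
- **That formulation selection would be distorted.** Protocol 9.1 and 9.2.2.1 tie selection to the exploratory non-inferiority analyses, and the GMC- and GMT-ratio shells use available results. Table 14.2.2.3 makes no between-group comparison, and Month 2 testing is planned at 96 in every group.

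**Conclusion.** The point holds for Month 2. If the shell is programmed as written, neutralizing seropositivity and the baseline-seronegative rows would read about 36-44% when the tested women are all positive. The percentage above the ULOQ would be diluted in the same way. At Month 7, and at Month 3 in the first interim analysis, the error lasts only as long as PBNA testing is incomplete.

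The size rests on three assumptions: a PPS of about 216 per group at Month 2, borrowed from Month 7; either no loss or a 20% loss among the 96 tested, which the documents do not specify for this subset; and complete positivity, chosen only to make the dilution visible. A different Month 2 PPS size would move the figures but not the conclusion, provided the PPS is well above the number tested. The damage is limited to descriptive percentages and their intervals, but the rule as stated gives a wrong result and conflicts with the SAP's own text.

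**What to change.** In Table 14.2.2.3, define N as PPS participants with an available PBNA result for that antigen at that visit, within pre-vaccination status. Use this N for n (%), the Clopper-Pearson interval and the count above the ULOQ, and add a line stating the percentage denominator. State the same denominator in SAP 16.2.3.4.

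Applying the same wording to the IgG shells (Tables 14.2.1.1 and 14.2.1.2) is optional consistency: IgG is run in all participants, so only sporadic missing results would matter there.

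The cost is one footnote and one SAP sentence, with matching programming. No new data, samples or analyses are needed.
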